## 9. LISTINGS

- List of patients.
- List of patients with adverse events.
- List of patients with adverse reactions.
- List of patients with serious adverse events.
- List of patients with serious adverse reactions.
- List of patients with adverse events (CTCAE Grade  $\geq 3$ ).
- List of patients with adverse reactions (CTCAE Grade  $\geq 3$ ).
- List of deaths (for which the causal relationship was not ruled out).
- List of deaths (for which the causal relationship was ruled out).
- List of patients with adverse reactions among children.
- List of patients with adverse reactions among the elderly.
- List of patients with adverse reactions among pregnant and parturient women.
- List of patients with adverse reactions among patients with off-label use.
- List of patients with adverse reactions among patients not meeting criteria for proper use.
- List of patients with adverse reactions among patients with hepatic dysfunction.
- List of patients with adverse reactions among patients with renal dysfunction.
- List of patients with adverse reactions among patients with a history of hepatitis B, tuberculosis, and herpes zoster [major investigation].
- List of patients with adverse reactions among patients with hepatic dysfunction (mild).

- List of patients with adverse reactions among patients with hepatic dysfunction (moderate).
- List of patients with adverse reactions among patients with hepatic dysfunction (severe).
- List of patients with adverse reactions among patients with hepatic dysfunction (hepatic transplant).
- List of patients with interstitial lung disease [major investigation].
- List of patients with a wide range of related events suspected of interstitial lung disease [major investigation].
- List of patients with dyspnea [major investigation].
- List of patients with diabetes mellitus/hyperglycemia [major investigation].
- List of patients with hypersensitivity reaction [major investigation].
- List of patients with diarrhea [major investigation].
- List of patients with hypophosphatemia [major investigation].
- List of patients with hypokalemia [major investigation].
- List of patients with hypercholesterolemia/hyperlipidemia [major investigation].
- List of patients with infection [major investigation].
- List of patients with intracerebral hemorrhage [major investigation].
- List of patients with abnormality in wound healing [major investigation].
- List of patients with mucositis-related adverse events [major investigation].
- List of patients with skin disorder [major investigation].
- List of patients with acute renal failure [major investigation].
- List of patients with gastrointestinal perforation [major investigation].

- List of tumor response.
- List of whether criteria for proper use are met.
- List of whether criteria for proper use are met (corporate reference values are used as reference laboratory test values).
- List of chest CT.

## 10. APPENDICES

### 10.1.1. Patient Demographics To Be Used To Evaluate Safety And Efficacy

#### Nominal scale

Item	Category	Remarks
Sex	Male, Female	
Age 1	<15 years, ≥15 to < 65 years, ≥65 years	
Age 2	<45 years, ≥45 to <55 years, ≥ 55 to <65 years, ≥65 to <75 years, ≥75 to <85 years, ≥85 years	
Age 3	<15 years, ≥15 years	
Age 4	<65 years, ≥65 years	
Body surface area (m  )	<1.2, ≥1.2 to <1.4, ≥1.4 to <1.6 ≥1.6 to <1.8, ≥1.8	
BMI	Low weight (<18.5), Ordinary weight (≥18.5 to <25.0), Obese Class I (≥25.0 to <30.0), Obese Class II (≥30.0 to <35.0), Obese Class III (≥35.0 to < 40.0), Obese Class IV (≥40.0)	
Inpatient/outpatient status	Inpatient, Outpatient	
Past medical history	Absent, Present	
Past medical history (lung disease)	Absent, Present	
Past medical history (interstitial lung disease)	Absent, Present	
Past medical history (hepatitis B, tuberculosis, and herpes zoster)	Absent, Present	
Past medical history (diabetes mellitus)	Absent, Present	
Complications	Absent, Present	
Complication (lung disease)	Absent, Present	
Complication (interstitial lung disease)	Absent, Present	
Complication (hepatitis B, tuberculosis, and herpes zoster)	Absent, Present	

### Nominal scale

Item	Category	Remarks
Complication (diabetes mellitus)	Absent, Present	
Hepatic dysfunction	Absent, Present	
Severity of hepatic dysfunction	Mild, Moderate, Severe	
Renal dysfunction	Absent, Present	
Severity of renal dysfunction	Mild, Moderate, Severe	
ECOG Performance Status	0, 1, 2, 3, 4	
Karnofsky Performance Status	10-20, 30-40, 50-60, 70-80, 90-100	
Risk classification (MSKCC Risk)	Good (0 of 5 items), Intermediate (1 to 2 of 5 items), Poor (3 to 5 of 5 items)	
Risk classification (Modified Risk)	Low risk (0 to 2 of 6 items), High risk (3 to 6 of 6 items)	
Risk classification: Time from the diagnosis of renal cell carcinoma to the initial systemic chemotherapy <1 year	Yes, No	
Risk classification: Karnofsky Performance Status ≤70	Yes, No	
Risk classification: Hemoglobin < institutional lower reference limit	Yes, No	
Risk classification: Adjusted calcium >10 mg/dL	Yes, No	
Risk classification: LDH >1.5-fold of institutional upper reference limit	Yes, No	

**Nominal scale**

Item	Category	Remarks
Risk classification:	Yes, No	
Number of metastatic foci ≥2		
Target disease	Unresectable or metastatic renal cell carcinoma, Others	
Presence or absence of metastasis (at the initiation of treatment)	Absent, Present	
Number of metastatic foci (at the initiation of treatment)	0, 1, ≥2	
Site of metastasis (at the initiation of treatment)	Lung, Liver, Bone, Brain, Others	No test
Histopathologic diagnosis	Clear cell, Non-clear cell, Not performed	
Histopathologic diagnosis (description)	Clear cell, Granule cell, Chromophobe cell, Spindle cell, Cyst-associated renal cell, Cyst-derived renal cell, Cystic renal cell, Papillary renal cell, Others	No test
Disease stage (at the diagnosis of target disease)	STAGE0,STAGE1,STAGE2,STAGE3,STAGE4	
Duration of illness	≥0 to ≤12 months, ≥13 to ≤24 months, ≥25 to ≤48 months, ≥49 months	
Prior treatment history (history of surgery: primary focus)	Absent, Present	
Prior treatment history (history of surgery: nephrectomy) (partial or total resection of primary focus)	Absent, Present	
Prior treatment history (history of surgery: metastatic focus)	Absent, Present	

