1 OBJECTIVES

The objective of this study is to assess the following subject matters in patients treated with TORISEL 25 mg Injection (hereinafter called this drug) in post-marketing actual use conditions, thereby providing proper-use information.

- (1) To confirm the effectiveness and safety of this drug under actual use conditions
- (2) To examine the onset state of adverse events and potentially influencing factors (particularly, major investigation items)
- (3) To examine the onset state and potential onset risk factors of interstitial lung disease

[Conditions for approval]

A drug use investigation must be conducted with all the patients treated with this drug until the data from a specified number of cases are accumulated after the marketing of this drug in order to understand the background information on patients treated with this drug, collect the data on the safety and effectiveness of this drug as early as possible, and take necessary measures to ensure the proper-use of this drug.

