The number of patients with CTCAE Grade  $\geq 3$  adverse reactions and the incidence of CTCAE Grade  $\geq 3$  adverse reactions will be tabulated by SOC and PT by category shown below. •Further tabulation of serious adverse reactions” will be followed for categories.

- Seriousness;
- Known/unknown;
- Outcome;
- Timing of initial onset;
- Intervention;
- Administration of this drug;
- Duration of treatment;
- Total dose.

- **Further tabulation of adverse events**

The number of patients with adverse events and the incidence of adverse events will be tabulated by SOC and PT by category shown below. “• Further tabulation of serious adverse reactions” will be followed for categories.

- CTCAE Grade.

- **Further tabulation of unknown adverse reactions**

The number of patients with unknown adverse reactions and the incidence of unknown adverse reactions will be tabulated by SOC and PT by category shown below. “•Further tabulation of serious adverse reactions” will be followed for categories.

- Outcome.

- **Cumulative incidence of adverse reactions**

The cumulative incidence of adverse reactions will be graphically presented with the time to onset on the horizontal axis.

The cumulative incidence will be graphically presented in the same manner for interstitial lung disease, diabetes mellitus/hyperglycemia, hypercholesterolemia/hyperlipidemia, infection, mucositis-related adverse events, and skin disorder among major investigation items.

- **Cumulative incidence of CTCAE Grade  $\geq 3$  adverse reactions**

The cumulative incidence of CTCAE Grade  $\geq 3$  adverse reactions will be graphically presented with the time to onset on the horizontal axis.

The cumulative incidence will be graphically presented in the same manner for interstitial lung disease, diabetes mellitus/hyperglycemia, hypercholesterolemia/hyperlipidemia, infection, mucositis-related adverse events, and skin disorder among major investigation items.

- **Incidence of adverse reactions by patient demographic**

The number of patients with adverse reactions and the incidence of adverse reactions will be tabulated by item listed in “[Section 10.1.1. Patient demographics to be used to evaluate safety and efficacy.](#)”

Fisher’s exact test will be performed for nominal scale data and Cochran-Armitage test (exact method) for ordered scale data.

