Tabulation will be performed in the same manner for interstitial lung disease, diabetes mellitus/hyperglycemia, hypercholesterolemia/hyperlipidemia, infection, mucositis-related adverse events, and skin disorder among major investigation items.

For items using reference laboratory test values, results using corporate reference values will be tabulated in addition to results using institutional reference values.

- **Incidence of CTCAE Grade  $\geq 3$  adverse reactions by patient demographic**

The number of patients with CTCAE Grade  $\geq 3$  adverse reactions and the incidence of CTCAE Grade  $\geq 3$  adverse reactions will be tabulated by item listed in “[Section 10.1.1. Patient demographics to be used to evaluate safety and efficacy.](#)”

Tabulation will be performed in the same manner for interstitial lung disease, diabetes mellitus/hyperglycemia, hypercholesterolemia/hyperlipidemia, infection, mucositis-related adverse events, and skin disorder among major investigation items.

For items using reference values, results using corporate reference values will be tabulated in addition to results using institutional reference values.

- **Incidence of adverse reactions by medical history, prior treatment history, and concomitant therapy**

The number of patients with adverse reactions and the incidence of adverse reactions will be tabulated by category shown below.

The number of patients and incidence will be tabulated in the same manner for interstitial lung disease among major investigation items.

- Past medical history;
- Complications;
- Prior medications.

- **Incidence of CTCAE Grade  $\geq 3$  adverse reactions by medical history, prior treatment history, and concomitant therapy**

The number of patients with CTCAE Grade  $\geq 3$  adverse reactions and the incidence of CTCAE Grade  $\geq 3$  adverse reactions will be tabulated by category shown below.

- Past medical history;
- Complications;

- Concomitant medications;
- Non-drug therapies;
- Prior medications.
- **Subgroups**

Safety in the following subgroups will be analyzed.

1. Children (<15 years), adults ( $\geq 15$  years).
2. Elderly ( $\geq 65$  years), non-elderly (<65 years).
3. Presence or absence of pregnancy.
4. Presence or absence of hepatic dysfunction.
5. Presence or absence of renal dysfunction.
6. By indication.
7. By whether criteria for proper use are met.
8. History of hepatitis B, tuberculosis, and herpes zoster.
9. Severity of hepatic dysfunction.
10. Sex.

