### 8.2.7. Efficacy Analysis

- **Response rate and clinical benefit rate**

The number and percentage of patients by best overall response, the response rate and its 95% confidence interval, and the clinical benefit rate and its 95% confidence interval will be tabulated in the safety analysis set and efficacy analysis set.

The response rate is defined as the percentage of patients whose best overall response is CR or PR.

The clinical benefit rate is defined as the percentage of patients whose best overall response is CR, PR, or SD.

The best overall response is defined as the best response among recorded overall response.

Table 1 of “New Guideline for the Assessment of Treatment Effect on Solid Cancer (Response Evaluation Criteria in Solid Tumors [RECIST] Guideline)–Japan Clinical Oncology Group [JCOG] version in Japanese” will be used for overall response, but overall response based on combinations of tumor response not corresponding to the table because of unknown data and no entry of data was uniquely defined. Therefore, the

tabulation analysis is not in complete compliance with the guideline and uses the guideline for reference.

**Table 1. Overall Response Based on Combinations of Tumor Response in Target and Non-target Lesions Including the Presence or Absence of New Lesions**

Target lesion	Non-target lesion	New lesion	Overall response
HCR	CR	Absent	CR
CR	IR/SD	Absent	PR
PR	Other than PD	Absent	PR
SD	Other than PD	Absent	SD
PD	Any response	Any response	PD
Any response	PD	Any response	PD
Any response	Any response	Present	PD

The following tumor response will be converted as shown by the arrow.

Non-target lesion: Absent → CR, not entered → IR/SD.

New lesion: Not entered → absent.

Overall response not corresponding to any combination in Table 1 after the above conversion will be considered as “unassessable.”

In addition, tabulation will be performed in the same manner by category shown below.

For items using reference laboratory test values, results using corporate reference values will be tabulated separately from results using institutional reference values as necessary.

- Site of metastasis [none, lung, liver, bone, lung + 1 organ, lung + 2 organs, lung +  $\geq 3$  organs,  $\geq 2$  organs other than lung, others];
- Whether criteria for proper use are met [yes, no];

- Prior treatment history [IFN- $\alpha$ , IL-2, Sutent, Nexavar, Afinitor, others];

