**Nominal scale**

Item	Category	Remarks
Prior treatment history (history of radiation therapy)	Absent, Present	
Prior treatment history (history of non-drug therapy)	Absent, Present	
Prior treatment history (drug therapy)	Absent, Present	
Prior treatment history (description of drug therapy)	IFN- $\alpha$ , IL-2, Sutent, Nexavar, Afinitor, Others	No test
Whether criteria for proper use are met	Yes, No	
ECOG PS 0~2	Yes, No	
Neutrophil count $\geq 1.5 \times 10^9/L$ (1500/mm  )	Yes, No	
Hemoglobin $\geq 8$ g/dL	Yes, No	
Platelet count $\geq 100 \times 10^9/L$ (10 x 10  /mm  )	Yes, No	
Serum creatinine $\leq 1.5$ -fold of institutional upper reference limit	Yes, No	
BUN $\leq 1.5$ -fold of institutional upper reference limit	Yes, No	
Total bilirubin $\leq 1.5$ -fold of institutional upper reference limit	Yes, No	

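### SAP 10.1.1 codes metastatic site and prior drug as untested overlapping lists with no absent category, so the readable plan never sets ILD with lung metastasis, or with a given prior drug, against ILD without it

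*SAP*

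**What the plan says.** The protocol's third objective is "To examine the onset state and potential onset risk factors of interstitial lung disease". SAP 8.2.6 pursues it, in the readable text, mainly by tabulating adverse reactions over the items in 10.1.1. The testing rule is "Fisher’s exact test will be performed for nominal scale data and Cochran-Armitage test (exact method) for ordered scale data". The same section carries this over to ILD: "Tabulation will be performed in the same manner for interstitial lung disease, diabetes mellitus/hyperglycemia", and so on through six major investigation items.

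Two items in the nominal table of 10.1.1 matter here:

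- Site of metastasis at the start of treatment, with categories "Lung, Liver, Bone, Brain, Others" and the remark *No test*.
- "Prior treatment history (description of drug therapy"), with five named agents plus others, and the same remark.

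Neither list has an absent or none category. Neighbouring rows do have an absent/present split and no such remark: "Presence or absence of metastasis (at the initiation of treatment") and "Prior treatment history (drug therapy").

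For efficacy, SAP 8.2.7 uses a different coding of site, beginning "none, lung, liver, bone, lung + 1 organ, lung + 2 organs". That coding includes a none class and is not carried into the ILD tables.

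**The concern.** A risk-factor analysis needs two groups: patients with the factor and patients without it. A multi-response list gives only the first. The lung row shows ILD incidence among patients with lung metastasis, but no row shows it among the rest, and patients with several sites count in several rows, so the rows cannot serve as each other's comparators.

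The neighbouring tested rows ask different questions. Any metastasis, absent or present, puts a patient with bone disease only in the same group as a patient with lung disease. Any prior drug therapy pools all agents.

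Other lung-related factors get the format that is missing here. History of lung disease, comorbid ILD, baseline chest CT, pulmonary surgery and smoking are all two-category items without the *No test* remark. In all, 73 nominal items are open to testing, including the BUN threshold and non-drug allergies. If lung metastasis or one prior agent were associated with ILD, the plan would have no prespecified estimate of that association.

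**Working it through.** **1. The plan's own figures.** The study-size rationale (protocol section 3) reproduces:

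- At least one event at 1.0% incidence in 300 patients: 1 − 0.99^300 = 0.951.
- At least 40 ILD cases at 17.1% in 300 patients: P(X ≥ 40), X ~ Binomial(300, 0.171), = 0.968.
- 300 / (1 − 0.5) = 600 registered.

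The documents give no figure for any risk-factor comparison, so the rest is a feasibility check.

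**2. What the readable text delivers for ILD.**

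| Question | Where | Comparator given? | Test? |
|---|---|---|---|
| Any metastasis | 10.1.1 | Yes | Yes |
| Lung metastasis | 10.1.1 | No | No |
| Any prior drug therapy | 10.1.1 | Yes | Yes |
| One given prior drug | 10.1.1; also 8.2.6 by prior medication | No | No |

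The further ILD tabulation in 8.2.6 splits by history of lung disease and by abnormal baseline imaging, not by lung metastasis.

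**3. Would a present/absent test be informative?** Inputs from the documents: N = 600, ILD 17.1% (600 × 0.171 = 102.6, about 103 cases), two-sided 5%, Fisher's exact test. Assumptions, because the documents give none: the exposed share f and the risk ratio RR.

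Risk without the factor: p0 = 0.171 / (f × RR + 1 − f). Risk with it: p1 = RR × p0.

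Example, f = 0.6 and RR = 2.0: p0 = 0.171 / 1.6 = 0.107 and p1 = 0.214. That is about 77 cases among 360 exposed and 26 among 240 unexposed.

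Exact power, summing the two binomial distributions over all tables with Fisher p ≤ 0.05:

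| Exposed share | RR 1.5 | RR 1.75 | RR 2.0 |
|---|---|---|---|
| 10% | 33% | 58% | 79% |
| 20% | 49% | 78% | 93% |
| 30% | 57% | 85% | 96% |
| 50% | 57% | 84% | 95% |
| 60% | 54% | 81% | 94% |
| 70% | 46% | 72% | 87% |

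The lower shares are meant for single prior drugs and the upper ones for lung metastasis.

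**4. If ILD is rarer.** The plan's 40-case yield rests on 300 patients, and it assumes that half of the 600 stop before 12 weeks. As a pessimistic case, take half the rate: 8.55%, or 600 × 0.0855 = 51 cases. Power at 50–70% exposed is then 36–48% for RR 1.75 and 51–66% for RR 2.0.

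**The case against.** The strongest reply is that *No test* is right for these items. The categories overlap, so one Fisher test across them would count patients more than once. That stands: the flag is not the error. What is missing is the step that normally follows, splitting the list into separate two-category items.

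Second, the flag removes the test and not the tabulation. ILD incidence still appears for each site and each drug, and 8.2.6 tabulates ILD by prior medication as well. With complete data, the group without the factor follows by subtracting from the total. This also stands, and it makes the gap smaller. But the plan does not specify that subtraction, and SAP section 7 gives no rule for missing entries, which would otherwise fall silently into the unexposed group.

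Third, lung status is well covered by the other tested rows, the study is not confirmatory (SAP section 4), and the documents nowhere name lung metastasis or any prior drug as an ILD risk factor. That they are natural candidates is a judgement.

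A reader might infer two stronger claims that the documents do not support:

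- That these comparisons are made nowhere. Part of 8.2.6 is blacked out, and SAP section 1 records that some blacked-out tabulations were moved into 8.2.6 and 8.2.7. Only the readable text can be judged.
- That response and clinical benefit cannot be related to these factors either. SAP 8.2.7 displays both rates with 95% confidence intervals by lung-based site classes and by prior drug.

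**Conclusion.** The concern holds for ILD at the level of the single factor. In the readable SAP, no present/absent comparison of ILD is specified for lung metastasis or for any individual prior drug, although the third objective is about ILD risk factors and comparable lung-related items have one. This is a gap in coding, not an invalid analysis, and closing it is a worthwhile, inexpensive improvement.

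The comparison would be useful for a doubling of risk: about 87–95% power at 50–70% exposed and 79–96% at 10–30% exposed. For a risk ratio of 1.5 it would be weak, 33–57% over the whole range. These figures assume 600 analysed patients, 17.1% ILD, and the stated exposed shares and risk ratios. They fall clearly if ILD is rarer. A non-significant result should therefore be read through its confidence interval and not as absence of risk.

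**What to change.** In SAP 10.1.1, replace the two lists with nine [absent, present] items: lung, liver, bone and brain metastasis, and prior Sutent, Nexavar, Afinitor, IL-2 and IFN-alpha. Patients without any metastasis, or without any prior drug, belong in the absent group. State that a site or drug not recorded in a completed entry counts as absent, and that a blank entry is missing.

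At least for ILD, report for each item the incidence in both groups, a risk ratio or risk difference with 95% confidence interval, and Fisher's exact test under 8.1.3. That section gives an exact interval for a single percentage only, so the method for the comparative interval must be named.

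No new data are needed: protocol 6.1 already collects metastatic status and prior drug therapy. The cost is SAP wording, nine rows per outcome, and nine more exploratory p-values beside the existing 73 nominal items. If no association existed, those nine would add at most 9 × 0.05 = 0.45 expected chance findings per outcome.

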**Nominal scale**

Item	Category	Remarks
Prior treatment history (history of radiation therapy)	Absent, Present	
Prior treatment history (history of non-drug therapy)	Absent, Present	
Prior treatment history (drug therapy)	Absent, Present	
Prior treatment history (description of drug therapy)	IFN- $\alpha$ , IL-2, Sutent, Nexavar, Afinitor, Others	No test
Whether criteria for proper use are met	Yes, No	
ECOG PS 0~2	Yes, No	
Neutrophil count $\geq 1.5 \times 10^9/L$ (1500/mm  )	Yes, No	
Hemoglobin $\geq 8$ g/dL	Yes, No	
Platelet count $\geq 100 \times 10^9/L$ (10 x 10  /mm  )	Yes, No	
Serum creatinine $\leq 1.5$ -fold of institutional upper reference limit	Yes, No	
BUN $\leq 1.5$ -fold of institutional upper reference limit	Yes, No	
Total bilirubin $\leq 1.5$ -fold of institutional upper reference limit	Yes, No	

